**Figure 1: Cohort expansion and dose escalation plan**

The highest SEL24/MEN1703 dose level considered to be well tolerated and to have optimal PK and PD characteristics, will be called the RD and will be selected for further evaluation in Part 2.

#### 4.2. Part 2

Part 2 is designed to enroll patients at the RD identified in Part 1 based on recommendation by the DMC.

**Part 2** foresees the enrollment of patients to be treated at the RD (identified in Part 1 based on recommendation by the DMC) in the expansion cohorts defined below:

- The expansion cohort in 20 unselected relapsed or refractory AML patients patients (“*all-comers*”)

**NOTE: At the time this protocol version 12.0 is running the expansion cohort in “*all-comers*” AML patients has been already completed with 23 patients enrolled.**

- An additional expansion cohort (“*IDH mutants*”) will enroll approximately 20 relapsed or refractory AML patients harboring an IDH mutation (either IDH1 or IDH2).

The evaluable patients treated at the RD in Part 1 or in Part 2 may be also retrospectively included in exploratory safety/efficacy pooled analysis, including patients with comparable inclusion criteria.

Considering that IDH inhibitors are approved/available only in some of the participating countries, it is anticipated that the study will enroll both IDH inhibitor pre-treated and IDH inhibitor naïve patients. For this reason, the recruitment will aim to have a balanced distribution across the two sub-populations to explore the differences in SEL24/MEN1703 activity between pre-treated and IDH inhibitor naïve patients, if any.

Retrospective correlations between the clinical activity of SEL24/MEN1703 and relevant disease markers (e.g. CD25 expression, FLT3 mutational status, IDH1/IDH2 mutational status, others) may be included in the statistical analysis plan.

Subjects who have a suitable donor and achieve a response allowing them to undergo hematopoietic stem cell transplant (HSCT) per each institution’s assessment can undergo HSCT without leaving the study. However, SEL24/MEN1703 should be stopped and a preHSCT visit should be performed prior to starting the conditioning regimen for HSCT. SEL24/MEN1703 can be resumed after stem cell transplantation if all the following conditions are met:

- Subject is between 30 - 60 days post HSCT

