3.1. Changes from study protocol

All analyses detailed in this document are as specified in the protocol and subsequent amendments, no major changes from the protocol-planned primary analysis have been performed.

4. Study overview

MEN1703 is a dual kinase inhibitor targeting PIM (PIM1, PIM2, PIM3) and FLT3 kinases which will be supplied as formulated drug product in a gelatin capsule.

This trial was designed as a Phase I/II, open-label, multi-center, dose escalation study to estimate the MTD (or MAD) of SEL24/MEN1703 in patients with AML. At the end of Part 1 a RD of SEL24/MEN1703 was selected for further evaluation in Part 2. In Part 2 the safety and anti-leukemic activity of SEL24/MEN1703 was further assessed in the study population. The starting dose was 25 mg SEL24/MEN1703 taken orally QD for 14 consecutive days over a 21-day treatment cycle.

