Considering that IDH inhibitors are approved/available only in some of the participating countries, it is anticipated that the study will enrol both IDH inhibitor pre-treated and IDH inhibitor naïve patients. For this reason, the recruitment will aim to have a balanced distribution across the two sub-populations to explore the differences in SEL24/MEN1703 activity between pre-treated and IDH inhibitor naïve patients, if any.

Subjects who have a suitable donor and achieve a response allowing them to undergo hematopoietic stem cell transplant (HSCT) per each institution's assessment can undergo HSCT without leaving the study. However, SEL24/MEN1703 should be stopped and a preHSCT visit should be performed prior to starting the conditioning regimen for HSCT. SEL24/MEN1703 can be resumed after stem cell transplantation if all the following conditions are met:

- Subject is between 30 - 60 days post HSCT
- Subject has had successful engraftment as demonstrated by absolute neutrophil count (ANC) \geq 500/mm³ and platelets \geq 20000/mm³ without transfusions
- Subject does not have \geq grade 2 acute graft-versus-host disease
- Subject is in CR, CRi, CRh

Those subjects resuming treatment will follow the procedures listed under subsequent Cycle 3 Day 1 in the Assessments Schedule. Subjects who do not resume SEL24/MEN1703 will be followed for the applicable endpoints' assessment.

Finally, MRD status will be recorded immediately prior to the transplant and after the procedure whenever a bone marrow aspirate/biopsy will be collected (recommended every 2 months unless differently indicated by the treating physician based on actual patient's parameters).

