7.3. Analysis populations

The following analysis populations will be considered in the statistical analysis:

- **Safety population:** the safety set consists of all patients that have received at least one dose of SEL24/MEN1703.
- **DD population:** the dose determining set will consist of all patients in each cohort that have completed one cycle of treatment and patients that discontinued earlier due to a DLT occurring in this period. This population will be used for the dose escalation Part 1.
- **PK population:** all patients who received any dose of SEL24/MEN1703 and have sufficient data for PK analysis. Therefore, all subjects receiving study drug and having at least 1 measurable drug concentration will be included in the PK population. If there are subjects who do not have sufficient samples for the PK non-compartmental analysis (NCA), a modified NCA will be conducted in which some or all PK parameters may not be estimated for those subjects, but available PK concentrations will still be tabulated and graphed.

For some objectives (e.g. anti-leukemic or PD activity), a subgroup of patients of the safety set with respective baseline and post-baseline measurements will be used along with the safety population.

- **Efficacy population:** the efficacy set will consist of all patients in each cohort that have completed one cycle of treatment (considering both the treatment and the washout period - 21 days) and have taken at least 75% of the study drug during the first cycle.

Thus, anti-leukemic activity will be analyzed on both the safety and the efficacy population.

Patients who were screened but did not receive any treatment will be listed and will not be part of any summary table.

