11.2. Descriptive statistics

All study variables will be presented by cohort, dose and overall, by using the appropriate descriptive statistics according to the variable nature, unless otherwise specified:

- **Continuous variables:** number of non-missing observations, arithmetic mean, median, standard deviation (SD), minimum, maximum;
- **Categorical variables:** number of non-missing observations and column percentages (N, %);
- **Time to event variables:** number of non-missing observations, number and percentage of censored observations, 1st quartile, median and its 95% Confidence Interval (CI), 3rd quartile, Kaplan-Meier survival curves.

The behaviour over time of study variables will be summarised by cohort and overall as follows:

- **Continuous variables:** descriptive statistics for each time point of interest;
- **Discrete variables:** descriptive statistics for each time point of interest.

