12.1. Efficacy analysis

The Overall Survival (OS) is calculated as:

- In case of all-cause death:
 $OS = date\ of\ death - date\ of\ first\ study\ drug\ administration + 1;$
- In case of censored information not for drop-out:
 $OS = date\ of\ end\ of\ observation\ period\ (i.e.\ study\ end / end\ of\ survival\ follow-up) - date\ of\ first\ study\ drug\ administration + 1;$
- In case of censored information for drop-out:
 $OS = last\ date\ known\ alive - date\ of\ first\ study\ drug\ administration + 1.$

The Relapse Free Survival (RFS) is calculated as:

- In case of relapse or all-cause death:
 $RFS = date\ of\ relapse\ or\ death\ (whichever\ comes\ first) - date\ of\ first\ CR,\ CRi,\ CRh\ or\ CR_{MRD-} + 1;$
- In case of censored information:
 $RFS = date\ of\ last\ relapse-free\ disease\ assessment - date\ of\ first\ CR,\ CRi,\ CRh\ or\ CR_{MRD-} + 1.$

The Event Free Survival (EFS) is calculated as:

- In case of relapse, treatment failure or all-cause death:
 $EFS = date\ of\ relapse,\ disease\ progression,\ treatment\ failure\ (failure\ to\ achieve\ CR/CRh/CRi/CR_{MRD-}\ after\ at\ least\ five\ cycles\ of\ treatment)\ or\ death\ (whichever\ comes\ first) - date\ of\ first\ study\ drug\ administration + 1;$
- In case of censored information:
 $EFS = date\ of\ last\ relapse-free/treatment-failure-free/progression-free\ disease\ assessment - date\ of\ first\ study\ drug\ administration + 1.$

The Duration of Response (DoR) is calculated as:

- In case of relapse, progressive disease or death due to progressive disease:
 $DoR = date\ of\ relapse\ of\ any\ type/progressive\ disease/death\ due\ to\ progressive\ disease - date\ of\ first\ CR,\ CRi,\ CRh,\ CR_{MRD-},\ MLFS\ or\ PR + 1;$
- In case of censored information:
 $DoR = date\ of\ last\ relapse-free\ disease\ assessment - date\ of\ first\ CR,\ CRi,\ CRh,\ CR_{MRD-},\ MLFS\ or\ PR + 1.$

No formal statistical analysis will be performed on anti-leukemic parameters.

Anti-leukemic activity data will be collected throughout Part 1 and Part 2 and will be summarized by cohort, by dose and overall.

Measures of anti-leukemic activity will be computed on both safety and efficacy populations and they will include:

- Changes (absolute and %) in pre- and post-treatment levels of leukemic blasts in the peripheral blood and/or bone marrow;
- Number and percentages of patients who reported as best overall response one of the following: CRM RD-, CR, CRh, CRi, MLFS, PR, SD, PD;
- Duration of response (DoR);

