12.2. Subgroup analyses

Not applicable.

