12.3. Pharmacokinetic analysis

The PK analysis will be run on the PK population.

Plasma concentration values Below the Lower Limit Of Quantification (BLLOQ) will be set to zero before the t_{max} and to “missing” after the t_{max} . Plasma concentrations reported as $>$ BLLOQ at time zero, when the subject has not previously been dosed, will be set to their real value. Data-replacements will be implemented by the Global Clinical Pharmacology and Pharmacometrics department. A footnote should be added to the listing, tables, and figures, in order to indicate the LOQ value.

If actual sampling time is missing, the nominal time will be used.

If the 24-hours post dose sample is collected after the intake of the following dose, the corresponding concentration will be reported in the listing with a FLAG and excluded from the PK parameter calculation.

If urine volume is missing, concentrations will be reported in the listing and no PK parameters will be calculated.

If samples are collected during an unscheduled visit, individual concentrations and PK parameter will be reported in the listing with a FLAG, but they will be excluded from the summary statistics.

All PK plasma and urine concentrations and PK parameters will be summarized by cohort, cycle, day, IDH mutational status, and nominal time point, and by dose, cycle, day, IDH mutational status and nominal time point, by using the following descriptive statistics:

- Number of non-missing observations (N),
- Arithmetic mean (AM) and its 90% confidence interval (CI), standard deviation (SD), coefficient of variation (CV%) and standard error (SE),
- Geometric mean (GM) and its 90% CI and GM CV%,
- Median,
- Minimum (min) and maximum (max).

Individual plasma concentration data versus time will be presented in a data listing and visualized as individual concentration-time plots. Individual urine concentration data will be presented in a data listing.

Actual times will be used for calculation of PK parameters and replaced by nominal times when missing. Plot of individual and aggregated concentration versus time curves will be generated with nominal times.

13. Tables, listings and figures

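### Recruitment to the IDH-mutant cohort is to be balanced by prior IDH inhibitor so that activity can be compared, but SAP 12.2 plans no subgroup summary and activity is grouped only by cohort, dose and overall.

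*SAP*

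**What the plan says.** **The aim.** Protocol 4.2 expects the IDH-mutant cohort to contain both patients already treated with an IDH inhibitor and patients who are naive to one. It sets a recruitment aim of balance between them "to explore the differences in SEL24/MEN1703 activity between pre-treated and IDH inhibitor naïve patients, if any". The synopsis and Protocol 8.13 (Estimated Sample Size) repeat this. SAP 5.1 carries it over: "the recruitment will aim to have a balanced distribution across the two sub-populations to explore the differences in SEL24/MEN1703 activity".

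**The analysis plan.** The whole of SAP 12.2 (Subgroup analyses) is "Not applicable". SAP 11.2 sets the general grouping: "All study variables will be presented by cohort, dose and overall". SAP 12.1 says that anti-leukemic activity data "will be summarized by cohort, by dose and overall". The efficacy tables in SAP 13.2.1 are Tables 3.1 to 3.3, and none names a split by prior IDH inhibitor.

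**What is already fixed.** SAP 7.3 settles the populations: "Thus, anti-leukemic activity will be analyzed on both the safety and the efficacy population". SAP 5.4.2 defines ORR. Protocol 8.9 permits an exact 95% confidence interval for Part 2 response. Protocol 5.3.1 requires all earlier AML treatment to be entered in the eCRF.

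**The concern.** The plan gives a reason for balancing recruitment, and the analysis chapter then provides no summary that serves it. Followed as written, the SAP pools the two groups that recruitment was meant to keep comparable.

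Two practical things are at stake.

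- **An unplanned split.** The data are collected, so someone can still make the split later. In an open-label study it would then be chosen after the responses are known, with the stratum definition, population and display left open.
- **Confounding with place.** The clarification note to inclusion criterion 4 (Protocol 3.1) admits naive patients only where no IDH inhibitor is approved or available in their country or site. The two strata may therefore differ by country as well as by treatment history. A split shown without country could be misread as an effect of prior treatment.

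**Working it through.** **1. The plan's own figure.** SAP 8 gives approximately 65 evaluable patients: 25 (Part 1) + 20 (all-comers) + 20 (IDH-mutant) = 65, which agrees. No sample-size figure is in dispute, and SAP 8 says that no formal calculation applies.

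**2. Is the split planned anywhere else?**

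| Place | Grouping or content | Prior IDH inhibitor against activity? |
|---|---|---|
| SAP 11.2, 12.1 | cohort, dose, overall | no |
| SAP 12.2 | none | no |
| SAP Tables 3.1 to 3.3 | response and time-to-event summaries | none named |
| SAP Table 1.9 | prior leukemia drugs by ATC code | baseline only |
| SAP 12.3 | IDH mutational status, PK only | different variable |
| SAP Listings 4.4, 4.6, 4.23 | previous treatment; response by timepoint | informal, patient by patient |

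On the PK row, SAP 12.3 states: "All PK plasma and urine concentrations and PK parameters will be summarized by cohort, cycle, day, IDH mutational status, and nominal time point". The SAP therefore adds a grouping factor where it wants one. Mutational status cannot stand in for treatment history, because inclusion criterion 1 requires every patient in this cohort to carry an IDH mutation.

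The protocol also says that retrospective correlations may be put in the SAP. That sentence concerns disease markers (CD25, FLT3, IDH1/IDH2 status). Prior inhibitor exposure has its own sentence.

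**3. What the cohort row hides.** Assumptions: 20 patients split 10/10 (the documents give no quota by prior inhibitor) and hypothetical responder counts. The intervals are Clopper-Pearson: for x of n, the lower limit is the 2.5% quantile of Beta(x, n−x+1) and the upper limit is the 97.5% quantile of Beta(x+1, n−x).

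The cohort row reads 4/20 = 20% (5.7 to 43.7%) in all three cases below.

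| Strata | Exact 95% CI, first stratum | Exact 95% CI, second stratum |
|---|---|---|
| 2/10 and 2/10 | 2.5 to 55.6% | 2.5 to 55.6% |
| 1/10 and 3/10 | 0.3 to 44.5% | 6.7 to 65.2% |
| 0/10 and 4/10 | 0 to 30.8% | 12.2 to 73.8% |

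If balance is not reached and a stratum has only 5 patients, 0/5 gives 0 to 52.2%.

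**4. How much could a split show?** Take the same true rate p in both strata. The chance of an observed gap of at least 20 points is the sum of Bin(a; n1, p) × Bin(b; n2, p) over all pairs with |a/n1 − b/n2| ≥ 0.20.

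| p (assumed) | 10/10 | 12/8 | 15/5 |
|---|---|---|---|
| 10% | 24% | 13% | 25% |
| 20% | 39% | 30% | 43% |
| 30% | 46% | 38% | 49% |

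A gap of that size is thus common when there is no difference. Even 0/10 against 4/10 is ambiguous: the Newcombe 95% interval for the 40-point difference is +4 to +69 points and excludes zero, while Fisher's exact test on the same table gives a two-sided p of 0.087. That table should not be read as showing that a difference is detectable.

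**The case against.** The strongest reply is that the protocol never turned this aim into an analysis.

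- **Background text.** SAP chapter 5 introduces itself as an overview of the protocol, so SAP 5.1 restates a hedged recruitment aim. A reader might infer that two analysis commitments in the SAP conflict. They do not: the mismatch is between a design purpose and an analysis chapter that does not serve it.
- **Consistency with Protocol 8.9.** That section also summarises activity by cohort, dose and overall, and Protocol Table 2 lists no comparison by prior inhibitor. A reader might conclude that SAP 3.1, with "All analyses detailed in this document are as specified in the protocol and subsequent amendments", is false. It is not. It speaks of the analyses that the SAP details, and the primary analysis is unchanged.
- **Listings.** Listings 4.4, 4.6 and 4.23 should let a reader match prior therapy to response for about 20 patients, so it would be wrong to say that nothing at all will be available. SAP 13.1 also describes the table index as indicative.
- **Little information.** At about 10 per stratum the result will be weak.

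All four stand as limits on the point, but none removes it. SAP 12.2 is explicit, a cross-read of listings has no agreed stratum definition, and low precision argues for showing intervals without a test.

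**Conclusion.** The gap is real and narrow. Both documents give comparison of activity between pre-treated and naive patients as the purpose of balanced recruitment, and the SAP plans no grouped summary of it. The populations, response definitions and basic summary statistics already exist; the grouping variable and its display are missing.

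The question is exploratory and is not a listed objective or endpoint. No primary or secondary conclusion depends on it. Two stronger readings are tempting and unsupported: that the trial fails one of its objectives, and that a split would reveal whether prior IDH inhibition changes activity. Protocol Table 2 rules out the first. The second fails on size, and on the eligibility rule that may tie stratum to country or site.

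The text comparison needs no assumption. The numerical illustration rests on an assumed 10/10, 12/8 or 15/5 split and on hypothetical counts and rates. The change is worth making because it is cheap and lets the trial describe what its recruitment was balanced for.

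**What to change.** Replace the entry in SAP 12.2 with text such as:

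> In the IDH-mutant cohort, best overall response and ORR are summarised by prior IDH inhibitor (pre-treated: any IDH1 or IDH2 inhibitor recorded as prior AML therapy; naive: none), in the safety and efficacy populations, as n and % with exact 95% confidence intervals. The same intervals are shown for the whole cohort. The summary is descriptive and no test is performed. Country is tabulated by stratum.

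Add the table to SAP 13.2.1. The whole-cohort interval is included because SAP 11.2 gives categorical variables only N and %, and the strata should not carry intervals that the cohort row lacks. Derive the stratum from the prior-therapy records in the eCRF: Table 1.9 is organised by ATC code, and nothing states that it isolates IDH inhibitors. Protocol 8.4 has the SAP signed before database lock, so the summary counts as planned only if it is added before then.

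**Cost.** One or two extra tables from data already collected, with very wide intervals, wider still in the smaller stratum if balance is not reached. The text covers response only; durations and survival by stratum are left out to keep it small. If the sponsor has dropped the question, SAP 3.1 should say so with the reason. That would remove the inconsistency but leave the question unaddressed.

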5.2. Schematic study design

A schematic representation of the drug administration schedule and the study design dose-escalation phase can be found below.

Figure 1: Study treatment outline

[figure not shown]
[figure not shown]

Figure 2: Cohort expansion and dose escalation plan

5.3. Study flow chart

Cycle	Screening ≤28-days	Cycle 1							Cycle 2			Cycle 3 onwards		Final Study Visit ¹⁷	Follow Up ¹⁸
		D1	D2	D3&4	D7 (±1)	D14 (±1)	D15	D17	D19	D1 (±2)	D7 (±1)	D14 (±1)	D1 (±2)	D14 (±1)	
Visit															
Demographics	X														
Medical history	X														
Inclusion/exclusion checks	X														
FSH and/or Pregnancy test ¹	X	X								X			X		X
ECOG PS	X									X			X		X
Vital signs ²	X	X								X			X		X
Physical examination ³	X	X								X			X		X
Clinical chemistry ⁴	X	X	X	X	X	X				X	X	X	X	X	X
Hematology ⁴	X	X	X	X	X	X				X	X	X	X	X	X
Coagulation ⁴	X	X	X	X	X	X				X	X	X	X		X
Lipid profile ⁴	X	X				X				X		X	X		X
Peripheral blasts ⁵	X	X				X						X		X	X
Urinalysis	X	X								X			X		X
Electrocardiogram ⁶	X	X			X					X			X		X
Echocardiogram (or MUGA scan)	X														
Bone marrow aspirate/biopsy ⁷	X												(X) [§]		(X)
Disease evaluation ⁸													(X) [§]		(X)
The genetic profile of AML cells ⁹	X												(X) [§]		(X)
PD biomarker blood sampling ¹⁰	X	X				X				X		X	X [§]	X [§]	
CYP2D6 phenotyping ¹¹	X														
CD25 Expression ¹²	X														
Mutational Status ¹³	X														
AML Karyotypic analysis	X														
Adverse events		X	X	X	X	X				X	X	X	X	X	X
Concomitant medication	X	X	X	X	X	X				X	X	X	X	X	X
Transfusion status	X	X	X	X	X	X				X	X	X	X	X	X
SEL24/MEN1703 administration ¹⁴		X - once daily dosing for 14 consecutive days in 21-day cycles													
PK sampling (blood) ¹⁵		X	X		X	X	X	X	X	X	X	X	X	X	
PK (urine collection) ¹⁶		X	X												
Follow-up assessments															X

General instructions:

- Informed Consent must be obtained using the current version of the PIS/ICF prior to commencing Screening.
- On dosing days, assessments should be performed prior to SEL24/MEN1703 dosing unless specified otherwise; tolerance windows for specific assessments are described below.
- (X) denotes an optional sample; please refer to Footnotes.
- X[§] denotes a sample not taken at every cycle; please refer to Footnotes.
- Additional assessments may be performed as clinically indicated.

Footnotes:

- A pregnancy test is required within 7 days prior to receiving study drug. Pregnancy test may be alternatively carried out at C1D1 visit prior to first SEL24/MEN1703 administration; results of the test should be available prior to receiving study drug. Additionally, a pregnancy test is required on the first day of each study cycle and at the Final Study Visit. If the Final Study Visit is performed before 30 days has elapsed from the last study drug administration, the pregnancy test shall be postponed when 30 days (+7 d tolerance) from the last study drug intake is elapsed (i.e. when no relevant drug systemic exposure is expected). A negative pregnancy test may

be confirmed by urine or blood test. Where a urine test is positive or equivocal, a blood test must be performed to confirm the result. Patients requiring confirmation of post-menopausal status will have FSH levels assessed at Screening.

2. Vital signs include temperature, systolic blood pressure, diastolic blood pressure, heart rate and respiratory rate.
3. Physical examination includes height and weight at Screening and only weight at the start of each cycle. After Screening, further assessments may be symptom-directed.
4. For complete list of Clinical chemistry, Hematology, Coagulation, and Lipid profile parameters please refer to Appendix E of the protocol. Coagulation parameters may be assessed from the Hematology sample. Should a patient develop coagulation abnormalities at any point during the study, a comprehensive evaluation of coagulation abnormalities will be performed immediately which may include, but not be limited to repeat PT/INR, APTT, fibrinogen, D-dimer, plus a peripheral blood smear, thrombin time, to be evaluated by the Investigator in conjunction with the patient's medical history, a physical examination and concomitant medication review. Repeat testing may be performed as clinically indicated, which may include additional parameters or time-points (please also refer to Appendix E of the protocol).
5. Assessment of blasts in peripheral blood will be carried out at Screening, C1 D1 pre-dose, C1 onwards at D14 (or last day of dosing in each cycle; -2 d tolerance from C3 onwards), and FSV. This assessment may be performed from the Hematology sample.
6. At C1 D1, the electrocardiogram assessment will be carried out pre-dose and at 4-6 h post dose.
7. Bone marrow aspirate/biopsy shall be taken at the following time points: at Screening, either as soon as peripheral lab results become consistent with an objective response or at C3 D1 whichever comes first, at a recommended frequency of every 2 cycles thereafter e.g. C5 D1, C7 D1, etc. (-2 d tolerance) or as clinically indicated, at relapse and FSV. In case of AML relapse following response to SEL24/MEN1703, a bone marrow aspirate/biopsy is highly recommended, whenever possible. Time-points described as (X)§ are recommended every 2 cycles, but not mandatory. Patients may not have the FSV assessment performed where they already have had a bone marrow assessment in the last month or have progressive disease. A bone marrow differential will be performed locally. An aliquot of bone marrow aspirate/biopsy will be centrally stored for future analysis (e.g. minimal residual disease), if any. Please refer to the Lab Manual for full details on bone marrow aspirates/biopsy collection, time-points, processing, storage and shipment.
8. Disease evaluation will be performed at every time-point (excluding Screening) where a bone marrow aspirate/biopsy is taken.
9. Bone marrow aspirate/biopsy taken during the study will be tested centrally for the genetic profile of AML cells. Please refer to the Lab Manual for full details on sample collection, time-points, processing, storage and shipment.
10. Blood sampling for PD biomarker assessments will be taken at Screening, C1 D1 pre-dose, C1 D1 2-6h post-dose, C1 D14 2-6h post-dose, C2 D1 pre-dose, C2 D14 2-6h post-dose, C3 D1 pre-dose, C3 D14 2-6h post-dose. All sample times are approximate and every effort should be made to take the samples as close to the specified time given and, where relevant, contemporaneously with blood sampling for PK assessments. For the C1 D1 and D14 a ±30 min window is allowed. Please refer to the Lab Manual for full details on PD biomarker sample collection, time-points, processing, storage and shipment.
11. CYP2D6 phenotyping will be assessed centrally on a blood sample collected at Screening.
12. CD25 expression will be assessed centrally on an aliquot of blood sample for PD biomarker assessment taken at Screening.
13. Mutational status (including at least FLT3 and IDH mutations) will be assessed locally at Screening.
14. SEL24/MEN1703 will be given once daily on D1-14 over 21-day treatment cycles. Doses shall be taken on an empty stomach (at least 2 hours after and 1 hour before eating).
15. Blood samples for plasma PK analysis will be taken at C1 D1 pre-dose, 0.5, 1, 2, 4, 6, 8, 10-14 and 24 h (C1 D2 pre-dose), C1 D7 at 4 and 8 h post dose, C1 D14 (or last day of dosing in cycle) pre-dose, 0.5, 1, 2, 4, 6, 8, 10-14 and 24 h (C1 D15), 72 h (C1 D17), 120 h (C1 D19), C2 D1 pre-dose (-1 d tolerance), D7 and 14 (or last day of dosing in cycle) at 2-6 h post dose, C3 onwards D1 pre-dose (-1 d tolerance) and D14 (or last day of dosing in each cycle) at 2-6 h post dose (-2 d tolerance). All sample times are approximate, and every effort should be made to take the samples as close to the specified time given and, where relevant, contemporaneously with blood sampling for PD biomarker assessments. For the C1 D1, D2, D7 and D14 a ±5 min window is allowed, for the C1 last day of dosing 24 h (C1D15), 72 h (C1D17) and 120 h (C1D19) samples, a ±2 h window is allowed. Please refer to the Lab Manual for full details on sample collection, time-points, processing, storage and shipment.
16. Part 1 only. Urine collection for PK analysis will be collected from the first dose of SEL24/MEN1703 until immediately prior to the second dose. Please refer to the Lab Manual for full details on sample collection, time-points, processing, storage and shipment.
17. Final study assessments to be conducted up to 30 d (+/- 2 d) from last dose of SEL24/MEN1703. Adverse events and concomitant medications must be assessed to 30 d from last dose of SEL24/MEN1703. Other assessments may be carried out between 7-30 d from last dose.
18. An assessment of each patient's disease status will be made approximately every 3 months from last dose of SEL24/MEN1703 for up to 1 year regardless of initiation of additional treatments to determine date of progression (where appropriate) and survival status.

